- Outpatient department – Female Pelvic Medicine and Reconstructive Surgery clinic (FPMRS clinic),
Department of Obstetrics & Gynaecology, Faculty of Medicine Ramathibodi Hospital

Trial registration:

The trial registration is planning to register on www.clinicaltrials.gov

Background and Significance:

Overactive bladder (OAB) is a prevalent condition characterized by urinary urgency, often associated with increased frequency and nocturia, with or without urgency urinary incontinence (UUI), and occurs in the absence of a urinary tract infection (UTI) or other apparent pathology (1). It affects about 12-20% of adults and increases incidence with age. It significantly impacts the quality of life, leading to physical discomfort, psychological stress, and social embarrassment with higher prevalence observed in women, particularly those in the menopausal transition or postmenopausal phase (2).

Menopause marks a significant hormonal shift in a woman's life, primarily characterized by the decline in estrogen production by the ovaries. Estrogen plays a crucial role in maintaining the structural and functional integrity of the lower urinary tract, vagina, and pelvic floor muscles. Due to these, the reduction in estrogen levels following menopause is considered a potential cause of pelvic floor disorders, including stress urinary incontinence (SUI), urgency urinary incontinence (UUI), and pelvic organ prolapse (POP), including OAB symptoms in menopausal women (3).

Estrogen therapy, particularly localized treatments like vaginal estrogen, has been utilized to alleviate urogenital symptoms associated with menopause (3). Vaginal estrogen has been shown to improve vaginal atrophy and increase urethral closure pressure (4). Moreover, it may alleviate OAB symptoms by restoring the health of the urogenital mucosa and improving bladder function. For clinical use, many studies have shown a significant reduction in urinary urgency symptoms, urinary incontinence, and increased maximal cystometric capacity (5, 6). However, the precise mechanisms by which estrogen influences bladder function and symptomatology remain not fully elucidated.

Recent advances in microbiome research have highlighted the significant role of the urinary microbiome (or urobiome) in urinary health and disease. Once considered sterile, the urinary tract is now known to host a diverse community of microorganisms that may influence urinary tract function and susceptibility to disorders like OAB (7). Alterations in the urinary microbiome composition, known as dysbiosis, have been associated with various urinary conditions, including overactive bladder, nocturia, interstitial cystitis and recurrent urinary tract infection (8). Understanding the impact of vaginal estrogen on the urinary microbiome of menopausal women with OAB could provide valuable insights into new therapeutic avenues and personalized treatment strategies. It may help clarify whether alterations in the urinary microbiome composition mediate the beneficial effects of estrogen on OAB symptoms.

This study aims to investigate the effect of vaginal estrogen therapy on changes in the urinary microbiome and its association with OAB symptom improvement in menopausal women. By exploring this relationship, we hope to enhance the understanding of OAB pathophysiology in menopausal women and contribute to developing more effective interventions targeting both hormonal and microbial factors.

Review Literature:			
Vaginal estrogen used in OAB treatment			
Author/Year/ Country	Study	Aim	Results
Cardozo LD et al (5) 2001 London, UK	
 • Randomized controlled trial • N = 110 • Vaginal 17β Estradiol VS Placebo • 12 weeks follow up 	Evaluate efficacy of 17 β Estradiol in treatment of postmenopausal women with Frequency, Urgency or UUI	Significant reduction in symptom of urinary urgency for women with sensory urgency
Simunic V. et al (6) 2003 Croatia	
 • Multicenter RCT • N = 1612 • Vaginal 17β Estradiol VS Placebo • 12 months follow up 	Determination of efficacy and safety of vaginal 17 β Estradiol in patients with urogenital symptoms	
In estrogen group
 
 • Improve urinary atrophy symptoms • Reduce urinary incontinence • Increase maximal cystometric capacity, first desire to void, strong desire to void

Overactive bladder/Urgency urinary incontinence and microbiome study			

 • Pearce MM, et al., 2014 (9) 
 ○ This study used Expand Quantitative Urine Culture (EQUC) techniques and 16s rRNA gene sequencing to analyze the trans-catheterized urine samples of patients with urgency urinary incontinence compared with the control group. ○ Results: 
 ▪ UUI microbiome was composed of increased Gardnerella and decreased Lactobacillus ▪ Nine genera were more frequently cultured from the UUI group (Actinobaculum, Actinomyces, Aerococcus, Arthrobacter, Corynebacterium, Gardnerella, Oligella, Staphylococcus, Streptococcus) ▪ More Lactobacillus gasseri in UUI group ▪ More Lactobacillus crispatus in control group 			

- Conclusion: bacterial communities in the urinary tract may be linked to UUI. Data suggest that potential important differences exist in urine microbiomes of women with and without UUI
- **Curtiss N, et al., 2017 (10)**
 - This study used 16s rRNA gene sequencing to analyze the urine samples from clean catch of patients with overactive bladder compared with the control group
 - Results:
 - Significant differences were found between the microbiomes of OAB patients and controls. *Lactobacillus* was more prevalent in controls (43%) compared to OAB patients (20%). Conversely, *Proteus* was more commonly found in OAB patients (23%) than controls (3%).
 - Conclusion: the female bladder has a diverse microbiome with significantly differences bacteria species present in overactive bladder patients and controls

Vaginal estrogen therapy in Overactive bladder and microbiome study

- **Thomas-White K, et al., 2020 (11)**
 - The quasi-experimental study aimed to determine the effect of vaginal estrogen treatment (0.5 g of conjugated estrogen twice weekly for 12 weeks) on urobiome diversity (using Expand Quantitative Urine Culture (EQUC) techniques) in postmenopausal women with overactive bladder.
 - Results:
 - A significant increase in *Lactobacillus* was detected in the bladder (10.8 vs. 25.1; P= 0.037) but not in the vaginal (P = 0.33), perineum (P = 0.56) or void urine (P = 0.28)
 - The change in *Lactobacillus* levels in the bladder was associated with modest changes in urgency incontinence symptoms (P = 0.02)
 - Conclusion: vaginal estrogen therapy alters the microbiome in different pelvic niches, remarkably increasing *Lactobacillus* in the bladder, which is associated with symptom improvement in postmenopausal women with OAB.

Objectives:

Primary Objective:

To evaluate the effects of vaginal estrogen on the level of *Lactobacillus* in the urine of postmenopausal women with OAB.

[figure not shown]
Secondary Objectives (if any):

1. To evaluate the effects of vaginal estrogen on urine microbiome in postmenopausal women with OAB.
2. To identify the association of alterations of urine microbiome after vaginal estrogen treatment with overactive bladder symptoms.

Study design/methodology:

Study design: Pre-post quasi-experimental study

Study flow diagram:

Note: The validated Thai version of OAB-q SF (12)

Study Population

Postmenopausal women with overactive bladder

Inclusion Criteria:

1. Natural or surgical menopause at least 1 year

2. Present with overactive bladder symptoms by using validated Thai version of OABSS (13) (score in No.3 \geq 2 and overall score \geq 3)
3. Absence of urinary infection
4. Post-void residual urine less than 100ml

Exclusion criteria

1. Currently or prior use of systemic HRT or vaginal estrogen within the past 3 months
2. Contraindication or allergy to estrogen therapy
3. Use of antibiotics, prebiotics and probiotics within the past 2 weeks
4. Currently on antimuscarinic or β 3 agonists medication or within the past 3 months
5. Pelvic organ prolapse greater than stage II

Study drug /Interventions <if applicable>:

17 β -estradiol 10 mcg (Femiest®, HAUPT PHARMA MUNSTER GMBH, Muenster, Germany)

1 tab daily for 2 weeks vaginally before bed, then 1 tab twice a week vaginally before bed until 12 weeks (Participants will be asked to bring the blister pack for pill count at the 12-week follow-up (checking compliance))

Comparator/Control <if applicable>:

None

Treatment Allocation and concealment:

None

Blinding (masking):

None

Participant timeline and Procedures:

Time	Study Visit	Procedures
Week 0	Screening and Enrollment	Eligibility screening, informed consent
Week 0	Baseline assessment	Demographic data, baseline symptom by OAB-q SF questionnaire, baseline urine sample collection for microbiome analysis by 16s rRNA gene sequencing.
Week 1-2	Intervention period	17 β -Estradiol Vaginal: Daily
Week 3-12	Intervention period	17 β -Estradiol Vaginal: 2 day per week
Week 12	Post-intervention assessment	Symptom evaluation by OAB-q SF questionnaire, urine sample collection for microbiome analysis by 16s rRNA gene sequencing.

Urine sample collection

Sterile urine collection procedures will be done by well-trained investigators on catheterization urine. The urine will be transferred immediately to the laboratory and placed at 4°C.

Outcomes/endpoints:

Primary Outcome

- Change in Lactobacillus abundance in urine after vaginal estrogen therapy

Secondary Outcome

- Change in urine microbiome diversity after vaginal estrogen therapy
- Association of change in urine microbiome with overactive bladder symptoms

Discontinuation/withdrawal criteria:

1. Adverse events or medical reasons
 - a. Severe Adverse Reactions: If a participant experiences severe or unmanageable side effects related to vaginal estrogen use (for example unexplained vaginal bleeding, severe irritation, or allergic reactions), they should be withdrawn from the study.
 - b. New Medical Conditions: development of new medical conditions that could interfere with the study outcomes for example cardiovascular issues
2. Non-Adherence to Treatment Protocol: Missed Follow-Up Assessments
3. Voluntary Withdrawal

Adverse Event Reporting:

1. Adverse events (AEs)
 - a. Definition: any unintended, unfavorable medical occurrence in a participant during the study, whether it is related to the study intervention (vaginal estrogen therapy) or not.
 - b. Examples: vaginal irritation, vaginal discomfort, vaginal discharge, bleeding, allergic reaction and possible systemic absorption of estrogen could lead to side effects such as breast tenderness or headaches.
 - c. Participant Responsibilities: Participants are instructed to immediately report any discomfort, symptoms, or health changes they experience during the study, regardless of severity.
 - d. Investigator Responsibilities: AEs and compliance will be inquired by follow-up phone calls from the investigator. Mild or moderate AEs will be managed by providing symptomatic treatment or observing the participant closely.

2. Serious adverse events

- a. Definition: Any event that results in hospitalization, life-threatening conditions, permanent disability, or death.
- b. Investigator Responsibilities: If a serious adverse event occurs, the participant will be withdrawn from the study, and immediate medical care will be provided. SAEs must be reported to the Ethics Committee and relevant regulatory bodies within 24 hours.

Statistical Analysis Plan:

- Descriptive statistics for baseline demographics and clinical characteristics were presented as mean and standard deviation or medians and interquartile ranges (IQRs) for continuous variables and frequency and percentage for categorical variables.
- Comparisons between pre-and post-intervention were tested using pair t-test or Wilcoxon signed-rank tests for continuous variables and chi-square or the Fisher exact tests for categorical variables.
- Association between changes in urine microbiome and changes in the OAB symptom were calculated using the Spearman rho test.

Microbiome study

- Alpha Diversity (within-sample diversity): measures provide insights into the richness (number of species) and evenness (distribution of species) within a sample.
 - Observed species, Chao1, Shannon, Simpson using QIIME software
 - Richness was calculated using Chao1 and observed species indices
 - Shannon and Simpson indices combined the interaction between richness and evenness
 - Wilcoxon rank sum test was applied to identify significant differences
- Beta Diversity (between-sample diversity): evaluates differences in microbial composition between samples.
 - Bray-Curtis and Uni-Frac (weighted and unweighted)
- Linear Discriminant analysis effect size (LEfSe): investigate microbial biomarkers between groups at the genus level

P-values <0.05 were considered statistically significant.

Sample size determination:

Using 2 dependent means formula for sample size calculation.

$$n = \frac{(z_{1-\frac{\alpha}{2}} + z_{1-\beta})^2 \sigma^2}{\Delta^2}$$

- From Pearce MM's study (2014), the median (IQR) percentage of lactobacillus in women with OAB was 13.6 (0-61.6); we expected the difference in mean percentage of lactobacillus after vaginal estrogen treatment was 25.
- Alpha (α) = 0.05, Beta (β) = 0.2
- The sample size was calculated = 27.
- Then, 10% data loss was added, the required sample size was 30.

Recruitment procedure:

- Menopausal women with a clinical diagnosis of overactive bladder (OAB) who meet the eligibility criteria will be recruited from the outpatient department – FPMRS clinic, Ramathibodi hospital.
- Interested patients will be directed appointed by research nurse to meet with the investigator.
- The investigator will give a detailed explanation, confirm eligibility through a detailed review of medical history and informed consent procedures.

Informed Consent Process:

1. Recruitment: Interested patients will be directed to meet with an investigator at the outpatient department – FPMRS clinic.
2. Detailed Explanation: The study's purpose, procedures, risks, and benefits are explained clearly.
3. Voluntary Participation: Emphasis is placed on the voluntary nature of participation and the right to withdraw at any time.
4. Signing the Consent Form: Participants sign the form after understanding the study and asking questions.
5. Ongoing Consent: Participants are reminded of their rights and informed of any protocol changes during the study.

Privacy and confidentiality (Data Management Plan):

1. The principal investigator and research collaborators will manage data and maintain patient confidentiality.
2. Assign Participant IDs to de-identify data and samples. The principal investigator will record information such as hospital numbers or names in a codebook.

3. Physical Storage: Any physical copies of data (e.g., paper forms and consent documents) will be securely stored in locked cabinets, with access limited to authorized personnel.
4. Biological Samples: Use urine samples only for outlined study purposes, store samples securely and label them with study ID and destroy samples according to biohazard regulations after use.
5. Digital Storage: All electronic data will be stored in encrypted databases, and any data transfers will occur over secure, encrypted networks. Regular backups will be performed to prevent data loss. Data will be stored for at least five years.
6. Participants can request access to or withdraw their data.

Ethical consideration:

- *Risks to participants and how to minimize the risks:*

1. Risks Related to Vaginal Estrogen Therapy
 - a. Potential risks: vaginal discomfort, allergic reaction, vaginal discharge
 - b. Risk minimization: Screen participants carefully to exclude those with contraindications to estrogen therapy, monitoring allergic reactions and educating participants
2. Risks Related to Urine Sample Collection by transurethral catheterization
 - a. Potential risks: discomfort, urinary tract infection and urinary tract injury
 - b. Risk minimization: Sterile urine collection procedures by the investigator who is well-trained, monitoring symptoms of urinary tract infection and educating participants

- *Direct Benefits to Participants*

Participants receive vaginal estrogen therapy as part of the study intervention at no cost. Vaginal estrogen therapy has been shown to alleviate symptoms associated with overactive bladder, such as urinary urgency, frequency, nocturia (nighttime urination), and urge incontinence.

- *Scientific or social value*

Supporting evidence of vaginal estrogen used in overactive bladder.

Understanding the changes in the urine microbiome caused by vaginal estrogen could allow for more personalized treatment strategies.

- *Justification if enrolling potentially vulnerable subjects.*

The study will not be conducted on vulnerable subjects.

- *Travel compensation and compensation for injury*

Participants will receive 1,000 Thai Baht per visit to compensate for travel expenses incurred while attending study appointments. This compensation is provided after each completed visit.

- *Plan of board consent*

None

Study Timeline:

Activities	2024					2025												2026			
	8	9	10	11	12	1	2	3	4	5	6	7	8	9	10	11	12	1	2	3	
1. Literature review and proposal preparation																					
2. Proposal submission and approval																					
3. Data collection and analysis																					
4. Manuscript writing and analysis																					

Budget:

Expense	Estimated cost/unit	Estimated cost
Participant Compensation	1000 Baht/visits	60,000 Baht
Intervention (Femiest®)	1197 Baht/box (18 tablets)	71,820 Baht
Urine catheterization	78 Baht/set	4,680 Baht
Urine microbiome analysis	5000 Baht/specimen	300,000 Baht
Total budget		436,500 Baht

References:

1. Haylen BT, de Ridder D, Freeman RM, Swift SE, Berghmans B, Lee J, et al. An International Urogynecological Association (IUGA)/International Continence Society (ICS) joint report on the terminology for female pelvic floor dysfunction. *Int Urogynecol J.* 2010;21(1):5-26.

2. Cardozo L. Textbook of Female Urology and Urogynecology: Clinical Perspectives. 5 ed. Staskin D, editor: CRC Press; 2003.

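### No masking of the sequencing laboratory or bioinformatics analyst to visit is described, and sample-exclusion, filtering and test choices are not fixed, so they could be made knowing which samples are post-estrogen

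*Combined protocol and SAP*

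**What the plan says.** The combined protocol and SAP describes a "Pre-post quasi-experimental study" with no comparator and no allocation. Under the heading that begins "Blinding (masking" it enters *None* and lists no roles.

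The participant timeline has a baseline urine sample and a second one at week 12: "Symptom evaluation by OAB-q SF questionnaire, urine sample collection for microbiome analysis by 16s rRNA gene sequencing". The primary outcome is "Change in Lactobacillus abundance in urine after vaginal estrogen therapy", so it comes entirely from the laboratory and the bioinformatics pipeline.

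Two items in the data management plan bear on labelling: "Assign Participant IDs to de-identify data and samples", and an instruction to "store samples securely and label them with study ID". The same section has the principal investigator record names and hospital numbers in a codebook. These are confidentiality measures. They do not say whether the visit appears on the tube or in the file sent for analysis.

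The Statistical Analysis Plan names software for alpha diversity ("Observed species, Chao1, Shannon, Simpson using QIIME software") but gives no minimum read depth, no rule for excluding a sample and no taxon or contaminant filter. For continuous pre-post comparisons it permits a paired t-test or a Wilcoxon signed-rank test, without saying which applies to the primary outcome or how the choice is made.

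**The concern.** The women and their clinicians cannot be masked in a one-arm study of an active treatment. The people who process the urine and the sequence data can be, and the plan does not provide for it.

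Sequencing itself is largely objective. The exposed steps are the discretionary ones: which samples are too poor to keep, where to set the read-depth cut-off, which taxa to remove and which paired test to report. The hoped-for direction is on record, because the sample size section expects a difference of 25 percentage points after treatment and the literature review cites an earlier rise in bladder *Lactobacillus* from 10.8 to 25.1. If someone who knows that direction also knows the visit, those steps offer a route to bias in the primary result. With about 27 analysable pairs, a few exclusions are enough to matter.

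**Working it through.** **1. What the plan covers**

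| Item | Stated in the plan? |
|---|---|
| Masking of laboratory or analyst to visit | No; the blinding entry is *None* |
| Tube label | Study ID; silent on visit |
| Read-depth cut-off | No |
| Sample-exclusion rule | No |
| Taxon or contaminant filter | No |
| Primary test | Two paired tests allowed, no rule for choosing |

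The gap is the combination: no masking to visit, and no rule that removes the discretion.

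**2. The plan's own sample size, to obtain a working SD**

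The plan does not state an SD. It cites a study in which the median (IQR) "percentage of lactobacillus in women with OAB was 13.6 (0-61.6"). Assuming the normal conversion, SD = IQR width / 1.35 = 61.6 / 1.35 = 45.6.

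With two-sided alpha 0.05, power 80% and a difference of 25:

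n = (1.960 + 0.842)² × 45.63² / 25² = 26.15, rounded up to 27.

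Allowing for 10% loss, 27 / 0.9 = 30. Both stated figures reproduce, so 45.6 is probably the SD the plan used. It is a cross-sectional spread, and using it as the SD of change is a further assumption.

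**3. Hypothetical example**

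The mean of +14.0 and the two values of -50 are invented for illustration.

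- All 27 pairs, mean +14.0, SD 45.6: t = 14.0 / (45.6 / √27) = 1.60 on 26 df, P = 0.12.
- Drop two pairs with change -50: new mean = (27 × 14.0 + 100) / 25 = 19.12.
- Sum of squares about zero: 26 × 45.6² + 27 × 14.0² − 2 × 50² = 54,355. Hence SD = √[(54,355 − 25 × 19.12²) / 24] = 43.4.
- t = 19.12 / (43.4 / √25) = 2.20 on 24 df, P = 0.037.

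**4. Worst case by simulation**

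Assumptions, none from the documents: no true effect, 30 pairs, normal differences with SD 45.6, a two-sided paired t-test at 0.05, and the k least favourable pairs dropped with the visit known (20,000 simulated trials).

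| Pairs dropped | Type I error | Upward bias in mean change (points) |
|---|---|---|
| 0 | 0.05 | about 0 |
| 1 | 0.08 | 3.3 |
| 2 | 0.14 | 6.0 |
| 3 | 0.22 | 8.6 |

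Three of 30 pairs is the plan's own 10% allowance for data loss. The table assumes deliberate selection of the worst pairs, so it is an upper bound for these numbers of exclusions under the stated assumptions. It does not predict what this team would do.

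**The case against.** Several stronger readings are tempting, and the documents do not support them.

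- *A reader might infer that processing choices will be made with the visit known.* The documents permit this but do not establish it. They do not say what the laboratory or the analyst is told.
- *A reader might infer that two tubes per woman force the visit onto the label.* A study ID alone cannot separate the two tubes, but any accession number would do so without showing the visit.
- *A reader might take* None *as a decision about every role.* It is a one-word entry that follows the same word under comparator and allocation. It may mean only that treatment is open-label.
- *A reader might argue that a comparator arm would cancel the discretion.* Choices driven by direction and made by unmasked staff could differ by arm, so they would not cancel there either. The missing control group is a separate and larger limitation.
- *A reader might take the P-values as evidence of bias here.* The example needs pairs to be dropped because of their *Lactobacillus* result. Exclusions unrelated to the result would not shift the mean systematically.

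The strongest point on the other side is that pre-specification would do most of the work: if the cut-off, exclusions, filter and test were fixed in writing beforehand, little discretion would remain to be masked. That is correct, and it is why the fix contains both elements. The plan as written has neither, so the objection narrows the point without removing it.

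**Conclusion.** The point holds as a cheap improvement. The plan describes no masking of laboratory or analyst to visit and leaves the discretionary processing steps and the primary test open, so those choices could be made knowing which samples are post-estrogen.

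The actual size of any bias cannot be derived from the documents. The P-values and the simulated error rates show only how sensitive about 27 to 30 pairs are to selective exclusion. They rest on an assumed SD of change of 45.6, normal differences and selection by result. There is no sign that such selection is intended. The sample size is unaffected, and masking would not allow a change over time to be attributed to estrogen in the absence of a control group.

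**What to change.** Replace the blinding entry with:

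> Participants and clinicians are not masked. Each urine tube carries a random code with no visit information. The sequencing laboratory and the bioinformatics analyst are masked to visit until the read-depth cut-off, sample exclusions, taxon filtering and primary test are fixed in writing. The code list is held by an existing team member who does not do the bioinformatics analysis.

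The last sentence matters because the data management plan has the principal investigator record the codebook and the principal investigator and collaborators manage the data, while the analyst is not identified. If the analyst were one of them, keeping the key in the same codebook might not mask that person. Amend the labelling item in the data management plan to match.

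The cost is small but not nil: about 60 coded labels (the budget's 300,000 Baht at 5,000 Baht per specimen gives 60 specimens, two for each of 30 women), an extra column in the code list and one person to hold it. No patient, visit or procedure is added.

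### Alpha diversity is a before/after comparison in the same women, but the plan names the unpaired Wilcoxon rank-sum test for it, against its own paired rule

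*Combined protocol and SAP*

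**What the plan says.** - **Design.** Under Study design/methodology the protocol states "Study design: Pre-post quasi-experimental study". The entry "Comparator/Control <if applicable>" is answered None. The participant timeline has urine collected for sequencing at week 0 and again at week 12.
- **Outcome.** The first secondary outcome is "Change in urine microbiome diversity after vaginal estrogen therapy".
- **General rule.** The Statistical Analysis Plan says: "Comparisons between pre-and post-intervention were tested using pair t-test or Wilcoxon signed-rank tests for continuous variables". The same sentence assigns "chi-square or the Fisher exact tests for categorical variables".
- **Alpha diversity.** Under Microbiome study, after listing Observed species, Chao1, Shannon and Simpson, the plan says: "Wilcoxon rank sum test was applied to identify significant differences".
- **Sample size.** The calculation is introduced with: "Using 2 dependent means formula for sample size calculation".

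**The concern.** Each woman contributes a week 0 and a week 12 value, so a change in diversity is a within-woman difference. The rank-sum test ignores which two values belong together. If a woman's two samples are positively correlated, the test uses too large a variance for the change. Its p-values are then too large, and a real change is more likely to be missed in a study of about 27 evaluable women.

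The plan also conflicts with itself. The general rule gives a paired test for this outcome and the specific line gives an unpaired one. An analyst would normally follow the specific line, which is the wrong one here. While both stand, the conclusion on diversity can depend on which line is followed, and the choice could be made after the data are seen.

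The chi-square/Fisher rule for pre/post categories has the same fault, because it counts a woman's two results as independent. No categorical outcome is named under Outcomes/endpoints, so this matters only if such a comparison is made.

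**Working it through.** **1. The plan's own figure.** The formula is n = (z₀.₉₇₅ + z₀.₈₀)² × SD² / Δ². The plan gives an interquartile range of 0 to 61.6 and a difference of 25, but no SD. Assuming SD = IQR/1.35 = 61.6/1.35 = 45.63:

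n = 7.849 × 45.63² / 25² = 26.15, rounded up to 27; and 27/0.9 = 30.

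Both stated figures reproduce. The two-independent-means formula with the same inputs gives 53 per group. The study was therefore sized on paired data.

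**2. Why pairing matters.** With common SD σ and within-woman correlation ρ, the mean change has variance 2σ²(1−ρ)/n. An unpaired test uses 2σ²/n. Its null statistic therefore has standard deviation of about √(1−ρ), and its true two-sided error is about 2[1 − Φ(1.96/√(1−ρ))]. At ρ = 0.3 this is 2[1 − Φ(2.34)] = 1.9%. At ρ = 0.5 it is 2[1 − Φ(2.77)] = 0.6%. The simulation below agrees.

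**3. Simulation.** Inputs: n = 27 pairs (from the plan), two-sided 0.05 (from the plan), bivariate normal data (assumed), ρ = 0, 0.3, 0.5, 0.7 (assumed), 20,000 trials per setting. Because the documents give no effect size for diversity, two scenarios were run:

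- Standardised paired effect held at 0.57. The raw shift is 0.57 × √(2(1−ρ)) = 0.81, 0.67, 0.57, 0.44 SD.
- Raw shift held at 0.81 SD.

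| | ρ = 0 | 0.3 | 0.5 | 0.7 |
|---|---|---|---|---|
| Type I error, rank-sum | 4.7% | 1.9% | 0.7% | 0.1% |
| Type I error, signed-rank | 5.0% | 5.0% | 4.9% | 4.7% |
| Power, paired effect held: rank-sum | 80% | 69% | 52% | 25% |
| Power, paired effect held: signed-rank | 79% | 80% | 79% | 80% |
| Power, raw shift held: rank-sum | 81% | 85% | 88% | 93% |
| Power, raw shift held: signed-rank | 80% | 92% | 98% | 99.9% |
| Tests disagree, paired effect held | 7.0% | 13.7% | 28.2% | 54.3% |
| Tests disagree, raw shift held | 7.0% | 8.9% | 9.5% | 7.3% |

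A separate run used the effect that gives a paired z-test 80% power, √(7.849/27) = 0.54. At ρ = 0.5 power was 47% for rank-sum and 74% for signed-rank, the same pattern. If the correlation were negative the error would reverse: at ρ = −0.2 the rank-sum type I error is 6.8%.

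**4. Categories (illustration only).** For an invented binary item moving from 30% to 60% positive, n = 27, 20,000 trials:

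| Power | correlation 0 | 0.3 | 0.5 |
|---|---|---|---|
| Exact McNemar | 49% | 64% | 83% |
| Fisher | 48% | 48% | 46% |
| Uncorrected chi-square | 59% | 60% | 62% |

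**The case against.** **It may be a naming slip.** The general rule and the sample size both treat the data as paired, so rank sum may simply have been written for signed-rank. If so, the analysis actually run might be correct. That is plausible, but the written plan still names the wrong test, and nothing elsewhere corrects it.

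**The line does not say what is compared.** The LEfSe line speaks of a search to "investigate microbial biomarkers between groups at the genus level", so an unpaired contrast might have been meant. That the two lines conflict is therefore an inference. It is a strong one: no second group, such as responders and non-responders, is defined anywhere, so week 0 against week 12 is the only comparison the design supports.

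**The size is uncertain.** This stands. The documents give neither the correlation nor a diversity effect. The largest losses arise where the raw shift shrinks from 0.81 to 0.44 SD. With the raw shift fixed, rank-sum power stays at 81% or more. The figures also assume normal data. They show the direction and a plausible range, not a forecast.

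**The error is conservative and concerns a secondary outcome.** This also stands for positive correlation: the cost is missed changes, not false claims.

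**The categorical point is hypothetical.** Agreed; it is a minor addition. At correlation 0 exact McNemar has about 10 points less power than uncorrected chi-square (49% against 59%), and at 0.3 only about 4 points more. The case for McNemar rests on the paired design, not on a gain in power at every correlation.

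**Conclusion.** The concern holds. As written, the plan assigns an independent-samples test to a paired secondary outcome and contradicts its own rule for continuous pre/post variables. That conclusion needs no assumption about correlation or effect size.

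The practical cost does need them. At correlations of 0.3 to 0.7, with 27 pairs and normal data, rank-sum loses 7 to 10 points of power (raw shift held) or 11 to 55 points (paired effect held). The documents give no basis for preferring either scenario, and at correlation 0 there is no loss.

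The primary Lactobacillus comparison falls under the paired rule, and the sample size is already based on paired data, so neither changes. This should be fixed before analysis, but it does not threaten the main result.

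**What to change.** 1. In the alpha-diversity section, replace the rank-sum line with the Wilcoxon signed-rank test on within-woman differences (week 12 minus week 0) for Observed species, Chao1, Shannon and Simpson. This agrees with the general rule.
2. In the general rule, replace chi-square/Fisher for pre/post categories with McNemar's test, exact where counts are small, and a marginal-homogeneity test where there are more than two levels.
3. If an unpaired comparison of diversity was intended, define the groups and list it separately from the before/after comparison.

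The cost is SAP wording and analysis code. No new data or participants are needed, and 27 and 30 stand.
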